5.5.1 Serum PK Parameters

The following PK parameters will be listed per visit, as data permits, from serum concentration data:

Parameter	Definition/Calculation	Units
C _{trough}	Observed trough serum BIIB092 concentration collected at end of dosing interval (before next infusion starts)	ug/mL

Individual PK parameter data will be listed. Descriptive statistics (N, mean, standard deviation, CV, median, minimum, and maximum) will be used to summarize the PK parameters by visit and dose. Geometric means (by visit and dose) will also be presented. Box plots and plots of individual C_{trough} over time will be provided.

5.6 Biomarker

The CSF PD evaluable set or CSF PD modified evaluable set as defined in [Section 3.1](#), will be used for the statistical modeling of CSF PD data.

5.6.1 Pharmacodynamics Analysis

The actual, change from baseline, and percentage change from baseline of CSF N-terminal tau will be summarized to evaluate pharmacodynamics effect after multiple IV infusions of BIIB092. For descriptive statistics, BLQ is imputed as LLOQ/2. For individual subject listings, BLQs are listed as BLQ. Summary statistics will be generated showing N, mean, median, standard deviation, Q1, Q3, minimum and maximum results over time by treatment group for CSF N-terminal tau for placebo-control and LTE period.

Mean (\pm standard error) plots of change from baseline of CSF N-terminal over time by treatment group and mean (\pm standard error) % change of CSF N-terminal tau over time by treatment group may be presented.

5.6.2 Structural MRI Analysis

No subjects reached week 226, the primary analysis timepoint for structural MRI. Therefore, structural MRI is not reported or statistically analyzed for the LTE period.

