2.2 Exploratory LTE Objectives and Endpoints

- To further evaluate the immunogenicity of BIIB092 after multiple doses in participants with MCI due to AD or with mild AD as measured by the incidence of anti-BIIB092 antibodies in serum over time up to Week 238.
- To further assess the effect of BIIB092 on disease progression as measured by fluid and radiological biomarkers, as well as additional clinical and health outcomes as measured by the following:
 - Changes over the placebo-controlled period and LTE period on the CDR-SB, MMSE, ISLT, Category Fluency and Letter Fluency tests from the DKEFS, DSST, Trails A, eCog, ADCS-ADL, FAQ, ADAS-Cog-13 (13-item), and NPI-10
 - Changes over the placebo-controlled period and LTE period on the ZBI, QoL-AD, and RUD-Lite
 - Changes over the placebo-controlled period and LTE period in CSF and blood biomarkers (for those who consent to participate in the optional CSF sampling substudy)
 - Changes over the placebo-controlled period and LTE period on 18F-MK6240 PET and MRI brain morphometric measures (for those who consent to participate in the optional PET substudy)
- To assess BIIB092 PK in serum (trough serum BIIB092 concentrations) and in CSF (for those who consent to participate in the optional CSF sampling substudy) from the samples collected at the visits indicated in the Schedule of Activities in participants with MCI due to AD or with mild AD.

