2.3 Study Design

This is a Phase 2, randomized, double-blind, placebo-controlled, parallel-group study consisting of a double-blind, placebo-controlled period and an LTE period.

The study includes 2 substudies to address exploratory study objectives: a tau PET substudy and a CSF sampling substudy. The tau PET substudy is mandatory at study sites that have access to the ¹⁸F-MK6240 PET radioligand and have the capability to perform ¹⁸F-MK6240 PET scans. During the placebo-controlled period, the CSF sampling substudy is mandatory at all study sites that do not have access to the ¹⁸F-MK6240 PET radioligand. Participants will provide consent during Screening to participate in at least 1 of these substudies during the placebo-controlled period. Participants enrolled in the LTE period and who are participating in the tau PET substudy are required to continue participation in the tau PET substudy. Participation in the CSF sampling substudy during the LTE will be optional for all study participants, although participation is encouraged.

This study will be conducted in participants aged 50 to 80 years, inclusive, with MCI due to AD or mild AD according to National Institute on Aging-Alzheimer's Association criteria. Participants must have amyloid beta positivity confirmed at Screening by either CSF sampling or an amyloid PET scan. Participants must also perform at least 1 standard deviation below the age-adjusted normative mean on either the ISLT or the International Shopping List Test Delayed Recall and have a CDR global score of 0.5 for MCI due to AD or 0.5 or 1 for mild AD, an MMSE score of 22 to 30 (inclusive), and a CDR Memory Box score of ≥ 0.5 .

During the dose-blinded LTE period, participants will receive BIIB092 by IV once every 4 weeks beginning at Week 80. Participants who were randomized to receive BIIB092 during the placebo-controlled period will continue to receive BIIB092 at the dose they were randomly assigned. Participants randomized to receive placebo during the placebo-controlled period will receive BIIB092 at the high dose (2000 mg) once every 4 weeks during the LTE period.

The total duration for participants who complete the placebo-controlled period and do not enter the LTE period will be approximately 99 weeks. For participants who complete both the placebo-controlled period and the LTE period, the total study duration will be approximately 247 weeks.

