4.1 LTE interim analyses at PC period database lock

The LTE interim analyses (IA) will be performed at the PC period database lock after the last patient out in the PC period. All the efficacy analyses described in [Section 5.3](#) will be performed with available efficacy data up to week 104 at the PC period database lock. Given the timeline of scheduled data collection, only a few subjects will have tau PET, CSF biomarker and health outcomes data collected in LTE visits. No LTE analyses of tau PET, biomarker or health outcomes will be included at LTE IA at PC period database lock.

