Week 116	813	[772, 953]	Week 196
Week 156	1093	[954, 1163]	Week 224
Week 176	1233	>1163	Week 238

Day 1 is the first infusion day in LTE period

Table 12. Visit Windows for tau PET data

Analysis visit *	Target visit day	Analysis visit window
Baseline	1	Most recent non-missing pre-dose value
Week 52	364	[120, 456]
Week 78	547	[457, 727*]
Week 152	1065	[728, 1324]
Week 226	1583	>1325

* 180 days after Week 78 target date.

CONFIDENTIAL

The information contained herein may not be used, disclosed, or published without the written consent of Biogen MA Inc.

Table 13. Visit Windows for C-SSRS data using Placebo controlled baseline

Analysis visit	Target visit day	Analysis visit window
Baseline	1	Most recent non-missing pre-dose value
Week 24	169	[2, 267]
Week 52	365	[268, 456]
Week 78	547	[457, the last day of the PC period ¹]
Week 104	729	[the start day of the LTE period ² , 813]
Week 128	897	[814, 981]
Week 152	1065	[982, 1149]
Week 176	1233	[1150, 1317]
Week 200	1401	[1318, 1492]
Week 226	1583	>1492

1. The end day of the placebo-controlled period is the last day before the first infusion in LTE, and is the last day in study for subjects who do not enter LTE.
 2. The start day of the LTE period is the day of first infusion in LTE period.

Table 14. Visit Windows for C-SSRS by Visit Summaries using LTE Baseline

Analysis visit	Target visit day	Analysis visit window	Protocol visit
Baseline	Most recent non-missing value prior to the first infusion in LTE	Most recent non-missing value prior to the first infusion in LTE	Week 78
Week 24	169	[the start day of the LTE period, 253]	Week 104
Week 52	337	[254, 421]	Week 128
Week 78	505	[422, 589]	Week 152
Week 104	673	[590, 757]	Week 176
Week 128	841	[758, 932]	Week 200
Week 152	1023	> 932	Week 226

Day 1 is the first infusion day in LTE period

Table 15. Visit Windows for safety MRI data with placebo-controlled baseline

Analysis visit	Target visit day	Analysis visit window
Baseline	1	Most recent non-missing pre-dose value
Week 28	197	[90, 281]
Week 52	365	[282, 456]
Week 78	547	[457, the last day of the PC period ¹]
Week 104	729	[the start day of LTE period ² , 911]
Week 156	1093	[912, 1338]
Week 226	1583	≥ 1339

1. The end day of the placebo-controlled period is the last day before the first infusion in LTE, and is the last day in study for subjects who do not enter LTE.
 2. The start day of the LTE period is the day of first infusion in LTE period.

Table 16. Visit Windows for safety MRI data with LTE baseline

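### SAP 5.6.2 drops all LTE structural MRI because no one reached Week 226, but that reason removes only the Week 226 visit

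*SAP*

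**What the plan says.** SAP 5.6.2 consists of the reason, "No subjects reached week 226, the primary analysis timepoint for structural MRI", and the consequence, "Therefore, structural MRI is not reported or statistically analyzed for the LTE period". It gives no count of scans at any LTE visit.

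The endpoint is set out in SAP 2.2. Under the exploratory objective "To further assess the effect of BIIB092 on disease progression as measured by fluid and radiological biomarkers" it lists "Changes over the placebo-controlled period and LTE period on 18F-MK6240 PET and MRI brain morphometric measures". Protocol Section 6 has the same MRI item. Neither place names a timepoint.

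The protocol's schedules of activities (Tables 1 to 4) place post-baseline brain MRI at Weeks 28, 52, 78, 104, 156 and 226. The treatment change comes at Week 80. SAP 2.3 states: "Participants randomized to receive placebo during the placebo-controlled period will receive BIIB092 at the high dose (2000 mg) once every 4 weeks" in the LTE.

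Protocol 13.3 says morphometry is assessed in every participant. Protocol 16.6.3 says the MRI results analysed may include morphometry, and that exploratory biomarker data are summarised descriptively by dose group. Protocol 16.1 says the two periods are analysed alike, apart from efficacy.

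The SAP keeps the safety reads of the same scans (5.4.9). Appendix I, Table 15, "Visit Windows for safety MRI data with placebo-controlled baseline", defines windows for Weeks 104 and 156.

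**The concern.** The reason does not reach as far as the decision. If nobody has a Week 226 scan, the Week 226 row is empty. Nothing follows about Week 104 or Week 156, and a descriptive by-visit summary needs no primary timepoint.

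The Week 78 and Week 104 scans lie on either side of the change from placebo to 2000 mg in the late-start group, while the early-start high-dose group stays on the same treatment. The rationale for protocol Version 3 says placebo participants were all moved to one dose to make the most of a delayed-start comparison. For morphometry, SAP 5.6.2 gives up that comparison and even the simple description of change.

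**Working it through.** **1. Scan timing.** The plan states no power or precision for this endpoint, so there is no figure to reproduce first. Study day = 7 × week + 1. LTE day = study day − 561 + 1, with Week 80 = Day 561.

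| Visit | Study day | LTE day | Weeks from switch, (day − 561)/7 |
|---|---|---|---|
| Week 78 | 547 | before LTE | −2 |
| Week 104 | 729 | 169 | 24 |
| Week 156 | 1093 | 533 | 76 |
| Week 226 | 1583 | 1023 | 146 |

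The study days match SAP Table 15 and the LTE days match SAP Table 16. Weeks 78 and 104 bracket the switch without Week 226.

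**2. How the SAP treats other measures with a Week 226 visit.**
- CDR-SB has a Week 226 window (Table 1). It is analysed at Week 104 at the interim and at the week of interest at the final analysis (5.3.3). SAP 4.1 says the interim efficacy analyses "will be performed with available efficacy data up to week 104 at the PC period database lock".
- Tau PET has LTE visits only at Weeks 152 and 226 (Table 12). Its by-visit summary is kept (5.6.3.1). Its first LTE visit is 152 − 104 = 48 weeks later than the first LTE MRI.
- Safety MRI is kept, with Weeks 104, 156 and 226 in Table 15.

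Only structural MRI is removed because Week 226 was not reached.

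**3. How many scans there may be.** The documents give no number. SAP 5.2.4 stops its infusion categories at 26. Protocol 11.1.1 gives 20 infusions through Week 76. Weeks 80, 84, 88, 92, 96 and 100 add 6, which makes 26. An early-start participant on a 4-weekly dose who missed none would have a 27th at Week 104. The full schedule would be 20 + 37 = 57. The categories therefore suggest, without proving it, that dosing ended at about Week 100 for those furthest along. The Week 104 count may be modest and Week 156 may be empty.

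**4. Precision at Week 104, early- versus late-start high dose.** 95% CI half-width in SD units = 1.96 × √(2/n). Difference detectable with 80% power = (1.96 + 0.84) × √(2/n). The share scanned is an assumption, applied to the planned 176 per group.

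| Share scanned | n per group | Half-width (SD) | Detectable (SD) |
|---|---|---|---|
| 10% | 18 | 0.66 | 0.94 |
| 25% | 44 | 0.42 | 0.60 |
| 50% | 88 | 0.30 | 0.42 |
| 80% | 141 | 0.23 | 0.33 |

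If the 654 randomised were split 1:1:2:2, each group would start from 654 × 2/6 = 218. The 10% to 80% range would then give half-widths of 0.59 to 0.21 SD.

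**5. The existing window.** Table 15 maps any scan from the first LTE infusion (nominally Day 561) to Day 911 to Week 104. That is 729 − 561 = 168 days before the target and 911 − 729 = 182 days after it. A scan on the day of the first LTE dose would count as Week 104. This may serve safety reads, but it would blur a comparison across the switch.

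**The case against.** The strongest defence has four parts.

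- **Week 226 was a considered choice.** The Version 4 amendment rationale calls the Week 226 scan key for pharmacodynamics and describes Week 104 as a critical safety assessment for those leaving placebo. This explains why Week 226 was preferred. It does not make it the only usable visit.
- **There may be little to report.** Step 3 supports this. An early-termination MRI is due only if withdrawal comes at least 6 months after the previous one, so someone who stopped before Week 104 with a Week 78 scan would generally have no LTE scan. SAP 4.1 refers to clinical efficacy data, not MRI. All of this stands, but SAP 5.6.2 does not argue from small numbers, and small n does not prevent a descriptive table.
- **The commitment is soft.** Protocol 16.6.3 says the MRI results may include morphometry, and 16.1 says LTE analyses are done as needed. That limits the point to an omission on an exploratory endpoint.
- **The comparators are imperfect.** CDR-SB is the primary efficacy endpoint, and a truncated tau PET table would be mostly placebo-controlled data. They show inconsistency, not a precedent for Week 104 imaging.

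A reader might also infer three stronger things that the documents do not support. One is that a whole LTE objective goes unanswered; tau PET, CSF N-terminal tau and the clinical scales under it are still analysed. Another is that morphometry from Weeks 28 to 78 is lost; a separate SAP, not supplied, covers that period. The third is that scans from about 218 participants per group lie unused; that is a randomised number, and no document says how many were scanned in the LTE.

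**Conclusion.** The point holds in limited form. The stated reason justifies an empty Week 226 row and no more. As written, one component of one exploratory LTE endpoint has no LTE result, for a reason that does not address the scans scheduled 24 and 76 weeks after the switch. The primary safety endpoint, the safety MRI reads and the other disease-progression measures are untouched.

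What a summary would yield depends on counts not in the documents. Across the assumed 10% to 80% scanned at Week 104, the half-widths in step 4 run from too wide for more than description to moderately informative. If almost no one was scanned at Week 104, omission could be defended, but on those counts and not on Week 226.

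**What to change.** Replace SAP 5.6.2 with a descriptive by-visit summary:

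- **Measures:** the morphometric measures used for the placebo-controlled period, named in the text, since this SAP names none.
- **Content:** n, observed value, change and percent change from placebo-controlled baseline, by LTE treatment group.
- **Visits:** Week 104, and Week 156 if reached, with Week 78 shown for reference. State that Week 226 has no data.
- **Window:** for Week 104, one centred on Day 729 in place of the Table 15 safety window. One option uses the midpoint between Weeks 78 and 104, (547 + 729)/2 = 638. Opening at Day 639 is 90 days before the target, and closing at 729 + 90 = Day 819 makes it symmetric.
- **Contrast:** if an early- minus late-start high-dose difference is shown, give a 95% CI and label it descriptive.

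The cost is a short SAP paragraph plus some extra image processing and analysis. The documents do not say whether LTE scans have already been processed for morphometry, so that effort cannot be sized here. The estimates will be imprecise if few were scanned, and the n column will make that plain.

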5.6.3 Tau PET Analysis

CONFIDENTIAL

The information contained herein may not be used, disclosed, or published without the written consent of Biogen MA Inc.

	Statistical Analysis Plan Long-Term Extension Period	V1.0
---	--	-------------

All tau PET analysis will be using tau PET evaluable set defined in [Section 3.1](#)

5.6.3.1 By visit summary

The baseline, change and percent change from baseline tau PET SUVR scores will be summarized by LTE treatment groups by visit for placebo-controlled and LTE period for each primary (Braak 1&2, Braak 3&4, and Braak 5&6) and secondary (Posterior composite, Temporal composite, Amyloid composite, Frontal cortex, Parietal cortex, Occipital cortex, Anterior cingulate cortex, Posterior cingulate cortex, Lateral temporal cortex, Inferior temporal cortex, Medial temporal lobe, Lateral temporal lobe) target region and primary reference region (Cerebellum (superior section eroded)). Visit window is defined in [Appendix I](#).

5.7 Anti-Drug Antibody Analysis

5.7.1 Analysis Methods for Anti-Drug Antibody Data

Anti-Drug Antibody (ADA) population will be used to analyze ADA data.

The baseline value is defined as the last available value prior to first dose of placebo or BIIB092 in placebo-controlled period. For subjects with missing baseline assessment, the most conservative approach will be taken and they will be considered negative for ADA at baseline.

For the definitions of treatment emergent positive, persistently positive, and transiently positive, please refer to the placebo-controlled SAP.

Summary table listing the number and percentage of all anti-BIIB092-positive and -negative antibody events by LTE treatment group and visits throughout the placebo-controlled and LTE active treatment period will be displayed.

In addition, a summary table of patients with treatment-emergent, persistent, and transient responses will be presented by LTE treatment group during the placebo-controlled and LTE active treatment period. A listing of anti-BIIB092 antibody results will also be provided.

Visit windows for by visit summaries

For ADA data that are summarized by visit, assessment from all scheduled visits, EOT visit, and unscheduled visits will be mapped to an appropriate analysis visit using a windowing scheme ([Appendix I](#)).

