3.2 Analyses Period

Depending on the purpose, different analyses will be conducted on the following study periods:

1. LTE period. Only data in the LTE period will be included in these analyses. This LTE analysis period will be applied to all the AE analyses, and the analyses will include all subjects who were dosed in the LTE period.
2. Placebo-controlled and LTE period. All the data in the placebo-controlled and LTE periods will be included in these analyses. This analysis period will be applied to analyses including, but not limited to all efficacy analyses and listings. The analyses will include all subjects who were dosed in the study including those who did not enroll into the LTE period. For example, line plot of CDR sum of box mean change from baseline over time. in the placebo-controlled and LTE period.
3. Placebo-controlled and LTE active treatment period. Active treatment period is defined as the study period(s) that a subject received BIIB092. For early start subjects – subjects who received BIIB092 in both placebo-controlled and LTE period, all the data (placebo-controlled and LTE periods) will be included in the analyses. For late start subjects – subjects who received placebo in the Placebo-controlled period and BIIB092 in the LTE period, only data in the LTE period will be included. This analysis period will be applied to majority of safety tables, and the analyses will include all subjects who were dosed in the study except for subjects who received only placebo in the placebo-controlled period and did not get dosed in the LTE period. An example is the incidence rate of adverse events in the placebo-controlled and LTE active treatment period.

Subjects to be included in a certain output is determined by both the analysis set and the analysis period. For example, the incidence table of adverse events in the LTE period will include subjects in the safety population for the LTE period, i.e., all randomized subjects who received at least one dose of study treatment in the LTE period. The incidence rate table of adverse events in the placebo-controlled and LTE active treatment period will include subjects in the safety population for the active treatment period, i.e., all randomized subjects who received at least one dose of study treatment in the active treatment period. In this SAP we do not separately define the analysis set in each analysis period.

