3.3 Study Treatment

For efficacy and health outcome analyses, the following LTE treatment groups of BIIB092 (per randomization) will be evaluated:

- low-dose (BIIB092 -125mg once every 4weeks or 375mg once every 12weeks)

CONFIDENTIAL

The information contained herein may not be used, disclosed, or published without the written consent of Biogen MA Inc.

	Statistical Analysis Plan Long-Term Extension Period	V1.0
---	---	-------------

- medium-dose (BIIB092 - 600mg once every 4 weeks)
- early start high-dose (BIIB092 - 2000mg once every 4 weeks)
- late start high-dose (BIIB092 - 2000mg once every 4 weeks)

For other analyses, such as safety, PK, PD, biomarker, and anti-drug antibody analyses, low dose group will be split out for different frequencies. The following LTE treatment groups of BIIB092 will be evaluated:

- low-dose 125mg once every 4weeks
- low-dose 375mg once every 12weeks
- medium-dose (BIIB092 - 600mg once every 4 weeks)
- early start high-dose (BIIB092 - 2000mg once every 4 weeks)
- late start high-dose (BIIB092 - 2000mg once every 4 weeks)

Since subjects in low-dose group and medium-dose group are taking the same treatment from the start of placebo-controlled period to the end of LTE period, so the subjects in these treatment groups are all considered as early start subjects. Late start subjects refer to subjects who were on placebo during placebo-controlled period then switched to high-dose (BIIB092 - 2000mg once every 4 weeks). Throughout this SAP, these study treatment schemes will be referred as LTE treatment.

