3.4 Dates and Points of Reference

The study day and baseline are defined for each analyses period respectively

1. LTE period

- Study Day 1: the date of the first dose of study treatment in the LTE period
- Study Day
 - For a date on or after Study Day 1

$$\text{Study Day} = (\text{Date of Interest}) - (\text{Study Day 1}) + 1$$
 - For a date before Study Day 1

$$\text{Study Day} = (\text{Date of Interest}) - (\text{Study Day 1})$$
- LTE baseline: the baseline value for the LTE period is defined as the most recent non-missing measurement collected prior to the first dose in the LTE period.
- Change from baseline will be defined as post-baseline value minus baseline value

2. Placebo-controlled and LTE period

- Study Day 1: the date of the first dose of study treatment in the PC period

CONFIDENTIAL

The information contained herein may not be used, disclosed, or published without the written consent of Biogen MA Inc.

- Study Day
 - For a date on or after Study Day 1
Study Day = (Date of Interest) – (Study Day 1) + 1
 - For a date before Study Day 1
Study Day = (Date of Interest) – (Study Day 1)
- PC and LTE baseline: the baseline value for the Placebo-controlled and LTE period is defined as the most recent non-missing measurement collected prior to the first dose in the PC period.
- Change from baseline will be defined as post-baseline value minus baseline value

3. Placebo-controlled and LTE active treatment period

- Study Day 1: the date of the first dose of BIIB092. For low-dose, medium-dose and early start high-dose subjects, this will be the date of first dose of BIIB092 in the placebo-controlled (PC) period; for late start high-dose subjects, this will be the date of first dose of BIIB092 in the LTE period.
- Study Day
 - For a date on or after Study Day 1
Study Day = (Date of Interest) – (Study Day 1) + 1
 - For a date before Study Day 1
Study Day = (Date of Interest) – (Study Day 1)
- Active treatment baseline: the baseline value for the active treatment period and is defined as the most recent non-missing measurement collected prior to study day 1.
- Change from baseline will be defined as post-baseline value minus baseline value

For data that are summarized by visit, assessment from all scheduled visits, EOS visit and unscheduled visits will be mapped to an appropriate analysis visit using a windowing scheme as describe in [Appendix I](#)

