Week 20	141	[128, 155]	Week 100
Week 24	169	[156, 183]	Week 104
Week 28	197	[184, 211]	Week 108
Week 32	225	[212, 239]	Week 112
Week 36	253	[240, 267]	Week 116
Week 40	281	[268, 295]	Week 120
Week 44	309	[296, 323]	Week 124
Week 48	337	[324, 351]	Week 128
Week 52	365	[352, 379]	Week 132
Week 56	393	[380, 407]	Week 136
Week 60	421	[408, 435]	Week 140
Week 64	449	[436, 463]	Week 144
Week 68	477	[464, 491]	Week 148
Week 72	505	[492, 519]	Week 152
Week 76	533	[520, 547]	Week 156
Week 80	561	[548, 575]	Week 160
Week 84	589	[576, 603]	Week 164
Week 88	617	[604, 631]	Week 168
Week 92	645	[632, 659]	Week 172
Week 96	673	[660, 687]	Week 176
Week 100	701	[688, 715]	Week 180
Week 104	729	[716, 743]	Week 184
Week 108	757	[744, 771]	Week 188
Week 112	785	[772, 799]	Week 192
Week 116	813	[800, 827]	Week 196
Week 120	841	[828, 855]	Week 200
Week 124	869	[856, 883]	Week 204
Week 128	897	[884, 911]	Week 208
Week 132	925	[912, 939]	Week 212
Week 136	953	[940, 967]	Week 216
Week 140	981	[968, 995]	Week 220
Week 144	1009	[996, 1023]	Week 224
Week 148	1037	[1024, 1051]	Week 226
Week 152	1065	[1052, the end day of the LTE period]	Week 238

CONFIDENTIAL

The information contained herein may not be used, disclosed, or published without the written consent of Biogen MA Inc.

Table 10. Visit Windows for ADA data using Placebo controlled baseline

Analysis visit	Target visit day	Analysis visit window
Baseline	1	See baseline definition in Section 3.7.1
Week 4	29	[2, 99]
Week 24	169	[100, 253]
Week 48	337	[254, 435]
Week 76	533	[436, the end day of the placebo-controlled period ¹]
Week 80	561	[the start day of the LTE period ² , 645]
Week 104	729	[646, 771]
Week 116	813	[772, 953]
Week 156	1093	[954, 1163]
Week 176	1233	[1164, 1303]
Week 196	1373	[1304, 1471]
Week 224	1569	[1472, 1618]
Week 238	1667	≥1619

1 The end day of the placebo-controlled period is the last day before the first infusion in LTE for subjects who enter LTE, and is the last day in study for subjects who do not enter LTE.
 2 The start day of the LTE period is the day of the first infusion in the LTE period.

Table 11. Visit Windows for ADA data using LTE Baseline

Analysis visit	Target visit day	Analysis visit window	Protocol visit
Baseline	Most recent non-missing value prior to the first infusion in LTE	Most recent non-missing value prior to the first infusion in LTE	Week 80
Week 24	169	[2, 253]	Week 104
Week 48	337	[254, 435]	Week 116
Week 76	533	[436, 631]	Week 156
Week 104	729	[632, 771]	Week 176

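### The SAP 5.7.1 antibody baseline for late-start participants precedes placebo, contradicts the SAP's own active-treatment baseline, and probably lets antibodies that predate BIIB092 count as treatment-emergent

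*SAP*

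**What the plan says.** **The ADA rule.** SAP 5.7.1 applies one baseline to every group: "The baseline value is defined as the last available value prior to first dose of placebo or BIIB092 in placebo-controlled period". A missing baseline counts as negative. It then says that "a summary table of patients with treatment-emergent, persistent, and transient responses will be presented by LTE treatment group", over the combined placebo-controlled and LTE active treatment period. The definitions of treatment-emergent, persistent and transient are left to the placebo-controlled SAP, which was not supplied.

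**The period.** SAP 3.3: "Late start subjects refer to subjects who were on placebo during placebo-controlled period then switched to high-dose" treatment. SAP 3.2 defines active treatment as time on BIIB092 and admits only LTE data for late start. SAP 3.4 sets Study Day 1 for that period: "for late start high-dose subjects, this will be the date of first dose of BIIB092 in the LTE period". The matching baseline is "defined as the most recent non-missing measurement collected prior to study day 1".

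**Other safety data.** Laboratory (5.4.3.1, 5.4.3.2), ECG (5.4.5.1) and vital-sign (5.4.6.1) analyses use the LTE baseline for late start and the placebo-controlled baseline for early start.

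**The ADA windows in Appendix I.** Table 10 uses the placebo-controlled baseline and sends the reader to Section 3.7.1, but Section 3 ends at 3.6. Its Week 80 window opens on the day of the first LTE infusion. Table 11 is titled "Visit Windows for ADA data using LTE Baseline" and takes the last value before the first LTE infusion, at protocol Week 80. Section 5.7.1 cites Appendix I but never says when Table 11 applies.

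**Sampling.** Protocol 13.6 schedules ADA samples on Day 1 and at Weeks 4, 24, 48, 76, 80 and later, all predose.

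**The concern.** For late start, the reporting period begins at first BIIB092 but the baseline is fixed at first placebo. Reactivity that arises between the two is neither baseline nor a response to the drug. If it is still present when the LTE begins, it enters the active-period table looking like a new conversion.

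This falls on one group. Early-start participants have no comparable placebo interval between baseline and first BIIB092, provided that the 375 mg every-12-weeks regimen starts with an active dose on Day 1. The late-start treatment-emergent count could therefore be raised for a reason unrelated to BIIB092. The SAP also supports two ADA baselines, and a programmer could defend either one.

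**Working it through.** There is no stated figure to reproduce. The check sets the rules side by side, tests the Table 11 windows and illustrates the size.

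**1. What each rule does with late-start results.** A late-start participant's Week 80 sample is drawn before any BIIB092. Table 10 nevertheless places it in a post-baseline LTE window, because that window opens on the infusion day.

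| Late-start pattern | Under 5.7.1 and Table 10 | With baseline before first BIIB092 |
|---|---|---|
| Day 1 negative, Week 80 predose positive | Negative to positive, with no BIIB092 exposure | Positive at baseline |
| Day 1 negative, Week 76 positive, Week 80 missed, Week 104 positive | Negative to positive | Positive at baseline |
| Day 1 missing, Week 80 predose positive | Baseline set to negative, so negative to positive | Positive at baseline |
| Day 1 negative, positive at Week 24 or 48, negative from Week 76 on | Not counted: placebo-period data are left out | Not counted |
| Day 1 positive | Positive at baseline | Depends on the Week 80 sample |
| Day 1 and Week 80 predose negative, Week 104 positive | Negative to positive | Negative to positive |

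Only the first three rows change to the late-start group's disadvantage.

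**2. Whether Table 11 can be used as it stands.** Week 80 is study day 561, so LTE day = study day - 561 + 1.

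| Protocol week | Study day | LTE day | Window labelled for that week | Window it falls in |
|---|---|---|---|---|
| 104 | 729 | 169 | [2, 253] | [2, 253] |
| 116 | 813 | 253 | [254, 435] | [2, 253] |
| 156 | 1093 | 533 | [436, 631] | [436, 631] |
| 176 | 1233 | 673 | [632, 771] | [632, 771] |
| 196 | 1373 | 813 | [772, 953] | [772, 953] |
| 224 | 1569 | 1009 | [954, 1163] | [954, 1163] |
| 238 | 1667 | 1107 | >1163 | [954, 1163] |

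On its target day, Week 116 is mapped with Week 104, and Week 238 with Week 224. No scheduled visit has its target day in the windows labelled for Weeks 116 and 238.

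**3. Size, on assumed rates.** The documents give no ADA rate on placebo and no number entering the LTE. Let p be the share of the placebo arm that enters the LTE positive after first turning positive on placebo. Expected number = 176 × p, with 176 the planned placebo arm:

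- p = 1%: 1.8
- p = 3%: 5.3
- p = 5%: 8.8

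The trial over-enrolled to 654. At the planned one-third share the placebo arm would be 654/3 = 218, and 176 would be 176/218 = 81% of it.

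**The case against.** A section specific to ADA normally takes precedence over a general definition, and a single pre-study baseline is a recognisable choice. The effect is also limited. The LTE endpoint is the incidence of antibodies over time, and the table of positives and negatives by visit needs no baseline. Listings cover both periods by default (SAP 5.2), so Week 80 status stays visible. ADA incidence is exploratory in the LTE.

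The precedence argument does not settle the matter. Table 11 is also specific to ADA, so the conflict lies within the ADA rules themselves. Section 5.7.1 claims conservatism only for its missing-baseline rule. The points on limited reach stand, and they keep this a modest issue.

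A reader might infer three stronger things that the documents do not support:

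- **Every antibody seen on placebo is counted.** SAP 3.2 leaves late-start placebo-period samples out, so one that has gone by Week 80 never enters the table.
- **Pre-existing reactivity is relabelled as a drug response.** If it is present on Day 1, it is already baseline-positive under 5.7.1.
- **The adverse event of special interest is distorted.** The protocol's Version 3 amendment summary separates antibody testing from the special-interest event called immunogenicity, and SAP 5.4.2.4 covers that event elsewhere.

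**Conclusion.** The contradiction is established from the text: 5.7.1 places the late-start ADA baseline before placebo, while Section 3.4, Table 11 and the other safety analyses place theirs before first BIIB092. The misclassification is a strong inference, not stated text, because the treatment-emergent definition is in a document not supplied.

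The effect is confined to antibodies first detected on placebo and still detectable at Week 80 predose or later, in the late-start column of one exploratory descriptive table. About 2-9 participants would be affected if 1-5% of the 176 planned placebo participants entered the LTE still positive. That is an upper bound for those rates on the planned arm: it assumes that all 176 enter and that none of the positives was already positive on Day 1. The rates are assumptions, and the true number could be near zero. The change is still worth making, because the present rule misattributes antibodies that predate the drug and the samples needed are already scheduled.

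**What to change.** 1. In 5.7.1, define the ADA baseline for late start as the last sample before the first BIIB092 infusion (Week 80 predose, or the last one before it). Keep the placebo-controlled baseline for all other groups. Word it by infusion rather than by date: the Section 3.4 wording, read by date, would exclude a predose sample taken on Study Day 1 itself.
2. In Table 10, treat the late-start Week 80 predose sample as baseline, not as a post-baseline visit.
3. Correct Table 10's reference to the absent Section 3.7.1.
4. State in 5.7.1 when Table 11 applies, and re-derive its windows so that protocol Weeks 116 and 238 fall in their own. One consistent way is to subtract 560 from Table 10's upper limits for Weeks 104 to 224 (771, 953, 1163, 1303, 1471, 1618). This gives [2, 211], [212, 393], [394, 603], [604, 743], [744, 911], [912, 1058] and ≥1059 for Weeks 104, 116, 156, 176, 196, 224 and 238. Each LTE day in the table above then falls in the right window.

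The cost is minor SAP and programming edits. No new data are needed.
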